7.3.4 Other variables

We will also obtain information on immigration and emigration, as well as date of birth and death status from the civil registration systems to be able to calculate the IRs in Substudies 2B, 3B, and 4B.

The interpretation of register-based variables with regard to missing information was discussed in section 7.3.1 and 7.3.2. For a few of the included register-based variables (e.g., sex and date of birth), all included persons should have information. We do not expect missing information on these variables; however, we will examine data to see whether missing information occurs. Missing data handling will be determined after review of the data, but before data from different registers are linked together (blinded to exposure to DL and outcome status) and will be described in a data control report, which will be submitted along with the study report.

7.4 Data Sources

The DL study will include register information from four Nordic countries – Denmark, Finland, Norway, and Sweden. In addition to a long history of collecting high quality information on births, deaths, immigration and emigration, disease incidence, and activities in the healthcare sector [Thygesen, L., et al 2011], exceptional opportunities to perform register-based research are driven by the unique PIC introduced in the Nordic countries in the 1960's and available to all persons with permanent residence in the Nordic countries [Pedersen, C. B. 2011]. The PIC makes it possible to link information at the individual level from several registers for scientific research purposes. The national prescription registers and national patient registers within each of the Nordic countries capture all the individual encounters of purchasing prescribed DL and allow sufficient longitudinal data to differentiate between first and recurrent seizures, as only first seizure will be analyzed, and to identify incident SVT and A-fib/flu cases. Person-specific use of DL will be elucidated from the

national prescription registers by obtaining information on redemption of DL prescription for each person [Furu, K., et al 2009]. Person-specific information on seizures, SVT, and A-fib/flu will be derived from the Nordic national patient registers.

Table 5 presents key information on the population-based health registers in the Nordic countries of relevance for the present study. Data will be available until and including 2015 for all countries. The data extraction period refers to the longest period for which data on exclusion variables (e.g., seizures, SVT, or A-fib/flu before baseline) can be obtained for.

Table 5 Overview of national health registers in the Nordic countries of relevance for the present study.

Register	Country			
	Denmark	Finland	Norway	Sweden
National prescription register	1995–2015	1994–2015	2004–2015	2005–2015
National patient register	1977–2015 (1)	1967–2015 (2)	2008–2015	1987–2015 (3)
Civil registration system	1968–2015	1967–2015	1964–2015	1965–2015
Study period	2001–2015 (15 years)	2001–2015 (15 years)	2008–2015 (8 years)	July 2005–2015 (11 years)
Data extraction period	1977–2015	1967–2015	2008–2015	1987–2015

(1) Contacts with outpatient clinics (incl. emergency departments) since 1995.

(2) Contacts with outpatient clinics (incl. emergency departments) since 1998.

(3) Contacts with outpatient clinics (incl. emergency departments) since 2001.

The national prescription registers include information on the date of prescription redemption, information on the purchaser, and information on the drug redeemed (e.g., ATC code, number of pills, daily dose, pack size, and number of packs purchased) [Kildemoes, H. W., et al 2011]. The Nordic national patient registers include diagnostic and treatment information for patients treated at the secondary and tertiary hospital level [Lynge, E., et al 2011] [Pukkala, E. 2011]. Clinical experts have been consulted on how to include information from the prescription and patient registers. Information on date of birth, immigration, emigration, and death will be obtained from the civil registration systems [Pedersen, C. B. 2011] [Pukkala, E. 2011].

7.4.1 Study Procedures

This is an observational, register-based study and pre-existing health-related national register data will be the sole data source. According to Danish, Finnish, Norwegian, and Swedish law, register-based studies can be carried out without consent from the individual subjects where the processing takes place for the sole purpose of carrying out statistical or scientific studies of significant public importance and where such processing is necessary in order to

carry out these studies. It is an absolute requirement that the publication of statistical or scientific results may never reveal the identity of individuals or otherwise compromise data subjects. We will obtain approval by the data agencies in the four countries before data management and data analyses will be performed.

7.5 Study Size

The proposed study will be performed in the framework of an observational design with the use of register-based data. The primary interest is to assess the association between current DL exposure in the general population and the outcomes (i.e., first seizure [Substudy 2B], first SVT [Substudy 3B], and first A-fib/flu [Substudy 4B]). For Substudies 2B, 3B, and 4B, a cohort study design among DL users will be used. The sample size in the present study will be fixed, as the study population for the association studies 2B, 3B, and 4B consists of all individuals in the four Nordic countries who have redeemed a DL prescription at least once. Hence, the aim of this section is to calculate the minimum detectable incidence rate ratio (IRR). Calculations concern Substudy 2B evaluating the association between DL use and first seizure, Substudy 3B evaluating the association between DL use and first SVT event, and Substudy 4B evaluating the association between DL use and first A-fib/flu. The actual annual IR of seizures, SVT, and A-fib/flu among current DL users is unknown and will be determined in the current study. Minimal detectable IRR were calculated based on a rearranged formula for sample size calculations developed by Bryant & Morganstein [Bryant, E. 1987] (Formula provided in Annex 7). The following are the parameters needed to calculate the minimum detectable IRR: the number of DL users in each age group (i.e., the fixed sample size); the proportion of exposed time (current exposure) and unexposed time (non-current/remote exposure) for DL users; the background event rates of seizures, SVT, and A-fib/flu; and the number of years included in the study along with statistical parameters and assumptions included in the equation (i.e., the significance level, power, and 1-sided versus 2-sided tests).

7.5.1 Fixed sample size

The number of DL users from each country has been estimated based on national drug sale statistics (Annex 1A). The annual unique number of DL users in Denmark, Finland, and Sweden for age groups 0–4, 5–19, 20–64, and ≥ 65 years is estimated to be 20,000, 86,000, 215,000, and 44,500, respectively. Data for Norway on DL prescriptions and seizures/SVT/A-fib/flu are available for a shorter time period; and therefore, Norway is not included in the calculations of the minimum detectable IRR. The number of annual unique DL users in the four countries is thereby slightly underestimated.

7.5.2 Proportion of current and non-current exposure time among DL users for the purpose of calculation of minimum detectable IRR

DL exposure (i.e., current DL use) is time-varying, and each person might have one or more periods as exposed and one or more periods as unexposed. Individuals in the study population (i.e., individuals who have redeemed at least one prescription of DL) are assumed to be exposed in a period following the date of DL purchase (i.e., current users). An estimate of the number of DL prescriptions redeemed per year in each age group was obtained from the feasibility study performed prior to developing the synopsis and the present protocol. For the minimum detectable IRR calculations, the mean number of prescriptions in each age group per year from the Danish data is used as an estimate of the average annual number of redemptions. The exposure period is then calculated as follows: (mean annual number of prescriptions in each age group*4 weeks (standard days' supply)) + 4 weeks grace period to account for intermittent use and a possible wash-out effect. Beyond this period, individuals are assumed to be unexposed (i.e., non-current users). The average number of prescriptions per year was estimated to be 1.50, 1.62, 1.78, and 2.30 for age groups 0–4, 5–19, 20–64, and ≥65 years, respectively¹.

Exposure periods for age groups 0–4, 5–19, 20–64, and ≥65 years were then calculated to be 10.00, 10.48, 11.12, 13.20 weeks, respectively. The proportion of exposed time in each age group is calculated as number of weeks exposed divided by number of weeks in a year (i.e., 52 weeks). For example, for age group 0–4 years, the proportion of exposed time is 10 weeks/52 weeks = 19%, and thus, the proportion of non-exposed or neither exposed nor unexposed time is 81%. Note: A simplified method was used to calculate exposed and unexposed person time for each age group for the purpose of estimating the minimum detectable IRR. The method for calculating exposed, unexposed, and neither exposed nor unexposed time for individuals for the study analysis is outlined in section 7.3.1.

7.5.3 Background event rate

The background incidence rate (i.e., IR) of seizures, SVT, and A-fib/flu was obtained from published studies [Hauser, W. A. and Beghi, E. 2008] [Orejarena, L. A., et al 1998] [Wilke, T., et al 2013]. IRs of seizure among unexposed individuals for age groups 0–4, 5–19, 20–64, and ≥65 years were estimated to be 65, 50, 40, and 40 per 100,000 person-years, respectively [Hauser, W. A. and Beghi, E. 2008]. The IR of SVT is reported to be 13/100,000 person-years for persons aged 19 years or younger, 27/100,000 person-years for persons aged 20–64

¹ By using Danish figures we might get conservative estimates of the minimal detectable IRR as mean number of prescriptions calculated for the feasibility study showed slightly lower means for Denmark compared to Sweden (figures from Finland and Norway were not available for these calculations). The average number of prescriptions per age group for the 20-64 and ≥65 year's age groups was calculated as the mean number of annual prescriptions (2001-2012) per age group using data from Denmark for ages ≥16 years. For the 5-19 year age group, the calculation was based on data from Denmark for ages 16-19. For the 0-4 year age group, the calculation was based on Swedish data from the feasibility study, which showed a tendency for a lower number of prescriptions in this age group compared to the older age groups.

years, and 122/100,000 person-years for persons aged 65 years or older [Orejarena, L. A., et al 1998]. Wilke et al. (2013) [Wilke, T., et al 2013] reported the incidence of A-fib to increase markedly with age with 0.0016 cases/1000 person-years in children (<15 years) and approximately 30 cases/1000 person-years for persons aged 80 years or older. No data on the epidemiology of flutter were available.

7.5.4 Number of years in the study

The maximum number of years (t) that an individual can be included in the study is 5 years for the age group 0–4 years and 12 years for the remaining age groups (≥ 5 years). The period of 15 years corresponds to the period where DL has been on the market. For the calculations of the minimum detectable IRR, we assume that individuals, on average, will be included in the study for a shorter period; and therefore, the maximum number of years included has been set to 2 years for ages 0–4 years and 6 years for ages ≥ 5 years.

7.5.5 Statistical parameters and assumptions

The minimum incidence rate ratio, $IRR > 1$, that can be detected is calculated using the following parameter values and assumptions:

Significance level, α : 0.05

Power, $1-\beta$: 0.80

1-sided test

7.5.6 Example of calculating the minimum detectable IRR

The mean number of DL prescriptions in the age group 0–4 years is 1.50 prescriptions. This gives an exposure period of $(1.50 * 4 \text{ weeks}) + 4 \text{ weeks} = 10 \text{ weeks}$. In this age group, 20,000 children have redeemed DL (i.e., the fixed sample size for this age group). Due to the exposure period of 10 weeks in this group, the proportion of the time exposed to DL is $10 \text{ weeks} / 52 \text{ weeks per year} = 19\%$. The background annual rate of seizures is 65/100,000 in this age group. It is assumed that individuals in this age group will be included in the study for an average of 2 years. When using a 1-sided test, significance level of 5% and power of 80%, the minimum detectable IRR will be 3.0.

Table 6 The minimum detectable incidence rate ratio (IRR>1) was calculated based on the Nordic population of SL users with at least one prescription of DL per year. Incidence rate (IR) of seizures is based on Hauser & Beghi (2008) [Hauser, W. A. and Beghi, E. 2008]. A 1-sided test, significance level of 5% and power of 80% have been used.

Age group (years)	Annual IR of seizures among unexposed individuals per 100,000 person-years	Mean number of individuals with at least one annual DL prescription in the Nordic countries	Estimated number of weeks exposed based on mean number of DL prescriptions per person	Minimum detectable IRR t=2 and 6 years (for age 0-4 years and age ≥5 years)
0-4	65	20,000	10.00	3.0
5-19	50	86,000	10.48	1.5
20-64	40	215,000	11.12	1.3
≥65	40	44,500	13.20	1.7

Table 7 The minimum detectable incidence rate ratio (IRR>1) was calculated based on the Nordic population of DL users with at least one prescription of DL per year. Incidence rate (IR) of SVT is based on Orejarena et al. (1998) [Orejarena, L. A., et al 1998]. A 1-sided test, significance level of 5% and power of 80% have been used.

Age group (years)	Annual IR of SVT among unexposed individuals per 100,000 person-years	Mean number of individuals with at least one annual DL prescription in the Nordic countries	Estimated number of weeks exposed based on mean number of DL prescriptions per person	Minimum detectable IRR t=2 and 6 years (for age 0-4 years and age ≥5 years)
0-4	13	20,000	10.00	8.2
5-19	13	86,000	10.48	2.1
20-64	27	215,000	11.12	1.4
≥65	122	44,500	13.20	1.4

Table 8 The minimum detectable incidence rate ratio (IRR>1) was calculated based on the Nordic population of DL users with at least one prescription of DL per year. Incidence rates (IR) for atrial flutter were not available; therefore, we base the calculations only on IR of A-fib obtained from Wilke et al. (2013) [Wilke, T., et al 2013]. A 1-sided test, significance level of 5% and power of 80% have been used.

Age group (years)	Annual IR of A-fib among unexposed individuals per 100,000 person-years	Mean number of individuals with at least one annual DL prescription in the Nordic countries	Estimated number of weeks exposed based on mean number of DL prescriptions per person	Minimum detectable IRR (for age 0-4 years and age ≥5 years)
0-4	1.6	20,000	10.00	54.0
5-19	3.8	86,000	10.48	3.4
20-64	168.9	215,000	11.12	1.6
≥65	2154.3	44,500	13.20	1.1

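### Table 8's minimum detectable IRR of 1.6 for A-fib at ages 20-64 does not follow from the Annex 7 formula, which gives 1.14; the child A-fib rate also differs tenfold between text and table

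*Protocol*

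**What the plan says.** Section 7.5 explains that the sample is fixed, so the section's purpose is to state the minimum detectable IRR for each outcome and age group. Section 7.5.5 sets the test: "Significance level, α : 0.05", "Power, $1-\beta$: 0.80", one-sided. Annex 7 gives the equation and sets follow-up at 2 years for ages 0-4 and 6 years for ages 5 and over, for all three outcomes.

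For ages 20-64, Table 8 (A-fib) has "20-64 168.9 215,000 11.12 1.6" and Table 7 (SVT) has "20-64 27 215,000 11.12 1.4". The columns are the background rate per 100,000 person-years, the number of users, the weeks exposed and the minimum detectable IRR. Table 6 (seizures) has a rate of 40 and an IRR of 1.3, with the same users and weeks.

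On the child A-fib rate, section 7.5.3 reports "0.0016 cases/1000 person-years in children (<15 years", and section 5 gives the same figure. The youngest row of Table 8 has "0-4 1.6 20,000 10.00 54.0", under a heading of per 100,000 person-years.

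**The concern.** At ages 20-64, Tables 6 to 8 differ only in the background rate. As it rises from 27 to 40, the detectable IRR falls from 1.4 to 1.3, as it should. At 168.9, more than four times higher again, it is said to rise to 1.6. With everything else fixed, more expected events cannot give worse detectability.

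The second oddity is that the child A-fib rate has the same digits in text and table but differs by exactly a factor of ten once the units are aligned.

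A-fib/flu is one of three primary hypotheses. Ages 20-64 hold 215,000 of the 365,500 annual users in section 7.5.1, about 59%. A reader who relies on 1.6 would think that IRRs between about 1.14 and 1.6 in this group lie beyond the study's planned reach.

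**Working it through.** **Inputs for A-fib, ages 20-64.** Rate 168.9 per 100,000, n = 215,000 and 11.12 weeks (Table 8); t = 6 years (Annex 7); one-sided α = 0.05 and power 0.80 (section 7.5.5).

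**Formula (Annex 7).** (p1 − p2)² = (Zα + Zβ)² [p1q1/(En) + p2q2/((1 − E)n)], with p2 = 1 − exp(−rate × t), E = weeks/52 and λ = p1/p2. Here (1.645 + 0.842)² = 6.18.

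**Check on the protocol's own cells first.**

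| Outcome | | 0-4 | 5-19 | 20-64 | ≥65 |
|---|---|---|---|---|---|
| Seizure | stated | 3.0 | 1.5 | 1.3 | 1.7 |
| | recomputed | 2.997 | 1.449 | 1.296 | 1.677 |
| SVT | stated | 8.2 | 2.1 | 1.4 | 1.4 |
| | recomputed | 8.227 | 2.019 | 1.369 | 1.355 |
| A-fib | stated | 54.0 | 3.4 | **1.6** | 1.1 |
| | recomputed | 52.4 | 3.385 | **1.136** | 1.075 |

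Eight of the other eleven cells agree to rounding. The remaining three (1.5, 2.1 and 54.0) are within about 4%; rounding E to 0.19 moves 52.4 to 53.0. The method is therefore the protocol's own.

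**The failing cell.**
- E = 11.12/52 = 0.2138, so En = 45,977 and (1 − E)n = 169,023.
- p2 = 1 − exp(−168.9 × 6/100,000) = 0.010083.
- At λ = 1.136, p1 = 0.011454 and (p1 − p2)² = 1.88 × 10⁻⁶. The right side is 6.18 × (2.463 × 10⁻⁷ + 0.591 × 10⁻⁷) = 1.89 × 10⁻⁶. The two sides meet.
- At λ = 1.6, the left side is 36.6 × 10⁻⁶ and the right side 2.5 × 10⁻⁶, so 1.6 is no solution.
- Power from the same formula is about 58% at 1.10, 80% at 1.136, 97% at 1.2 and above 99.9% at 1.6.

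**Could another choice give 1.6?**
- Two-sided test: 1.155.
- Pooled variance: 1.133.
- Log rate ratio: 1.132.
- t = 2 years: 1.245; t = 1 year: 1.360.
- Two-sided, 95% power and t = 1 year together: 1.552.

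None reaches 1.6. That value would need a rate of about 11.6 per 100,000, or about 14,700 users. Neither figure appears for this group.

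**Child A-fib rate.** 0.0016 per 1,000 × 100 = 0.16 per 100,000 in the text, against 1.6 in Table 8. The formula gives 52.4 at 1.6 and about 504 at 0.16. Expected background events in exposed time at ages 0-4 are 20,000 × 2 × rate × 10/52, which is 0.12 at 1.6 per 100,000 and 0.012 at 0.16. With so few events the normal approximation means little, and 504 is only an order of magnitude.

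The age bands differ (under 15 against 0-4), but this hardly explains the gap. Even with no A-fib at ages 5-14, a 0-4 rate of 1.6 is compatible with an under-15 rate of 0.16 only if ages 0-4 supply 0.16/1.6 = 10% of the under-15 person-time. If they supply about a third (an assumption: 5 of 15 single years of age), the under-15 rate would be about 0.5.

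**The case against.** The strongest reply concerns consequence. All DL users are included whatever Table 8 says, and no model, endpoint or follow-up rule depends on it. Section 7.5.2 calls its exposure calculation simplified, and section 7.5.1 leaves Norway out. The 20-64 error is conservative, because the protocol claims less sensitivity than its formula gives. What a null result excludes will be read from the estimated IRR and its confidence interval, not from a planning figure. All of this stands and limits the severity. It does not make 1.6 follow from the stated inputs.

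A reader might infer that Table 8 as a whole is unreliable. The documents do not support this: "5-19 3.8 86,000 10.48 3.4" and "≥65 2154.3 44,500 13.20 1.1" both reproduce, and 54.0 is within about 3% of what the table's own rate gives.

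A reader might also infer that the youngest group's 54.0 is about tenfold too optimistic. That holds only if the text's rate is the right one. The slip could equally be in the text, and the cited source is not at hand. Section 7.9 already calls the sample inadequate for A-fib in this age group, and that conclusion holds at either rate.

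**Conclusion.** The point holds for one cell and one inconsistency. The 20-64 A-fib cell is wrong as printed: 1.14 against 1.6, an excess of 0.14 rather than 0.60. This rests on the Annex 7 equation and on Table 8's inputs, including 168.9 per 100,000, being what the authors intended. If another input was meant, the row is still inconsistent and that input must be shown.

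The child A-fib rate is a tenfold contradiction between the text and Table 8. Which side is in error cannot be settled from the documents.

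Severity is minor to moderate. A stated detectability figure for a primary outcome is wrong in the largest user group, but the error is conservative and changes no analysis.

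**What to change.** 1. In Table 8, restate the 20-64 cell as 1.14, or state the input that yields 1.6. Give two decimals, because power at 1.10 is only about 58%.
2. Check the child A-fib rate against the cited source. If 0.16 per 100,000 is right, change the rate in the 0-4 row and either recompute the cell (on the order of 500) or, better, mark it as not assessable. If 1.6 per 100,000 is right, correct sections 5 and 7.5.3 and leave the row.
3. Leave the 5-19 and ≥65 A-fib cells as they are. Section 7.9 needs no change: it quotes neither 1.6 nor 54, and its one figure, 8.2 for SVT, reproduces.

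The cost is one table cell, plus either the 0-4 row or the rate in two text sections. No data, design or analysis changes.

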7.6 Data Management

The handling of data in the DL study involves six steps and requires applications and approvals for access to data in each of the four Nordic countries. In addition to the acquisition and management of data, a primary scientific coordinator will be responsible for the overall study and establishment of a joint Nordic study dataset. Four national scientific coordinators will be responsible for steps 1-4 in each country, whereas the Danish scientific coordinator also will be responsible for steps 5-6.

The handling of data is categorized into the following six steps:

- All national scientific coordinators will apply to the relevant agencies for permission to perform the study and to get access to data.
- All national scientific coordinators will facilitate the construction of the study populations:
 - Study population consisting of all DL users during the study period.
 - Study population consisting of all individuals with seizure during the study period and the years prior to the study period.
 - Study population consisting of all individuals with SVT during the study period and years prior to the study period.
 - Study population consisting of all individuals with A-fib/flu during the study period and years prior to the study period.

-
- All national scientific coordinators are responsible for acquiring and validating the datasets and will explore how the data can be combined from the registers. Data quality control includes but is not restricted to check for legal values for each categorical variable, check of consistency between dates (at least date of birth before all other dates and date of death after all dates), and check and advise on the handling of missing data. All national scientific coordinators will produce a data control report describing the checks performed. All national scientific coordinators will derive the final dataset from the data obtained from the registers by combining the registers according to the study designs. All national scientific coordinators will produce a data control report describing the checks performed of the final dataset, including reasons for modifications and exclusions. In this process, all national coordinators have to agree on the reasons for exclusion (e.g., missing value on crucial variables, chronological errors in the relation between dates, non-legal values of categorical variables, and extreme values of continuous variables). The national scientific coordinators should send the final data set and the data control reports that describe the data and provide suggestions on how to handle missing values and invalid codes to the Danish scientific coordinator. A template for the data control report will be provided by the Danish scientific coordinator and will include the following requirements:
 1. Information on known misclassification of each variable (e.g., underreporting, low sensitivity or specificity, categorization with obvious invalid values, etc.).
 2. Check for legal values for each categorical variable. Check for reasonable distribution of variables. Include advice on how to handle unexpected observations.
 3. Check for reasonable minimum, maximum, and central tendency (median, mean) for each continuous variable. Check for outliers must be performed (e.g., exploratory plots, such as box-whiskers plot). Include advice on how to handle unexpected observations.
 4. Check of chronological relation between date variables: At least date of birth before all other dates and date of death after all dates, but also reasonable relation of dates of diagnoses and prescriptions. Unexpected patterns should be described and solutions for handling such observations should be included.
 5. Check of missing information on variables and include advice on how to handle such observations (e.g., delete observations with missing information, put missing observations into a specific category, etc.).
 - The final datasets from Finland, Norway, and Sweden are transferred to Statistics Denmark where all subsequent data handling is done by the Danish scientific coordinator.

- The Danish scientific coordinator combines data as described by the document developed by all national scientific coordinators and the datasets from all countries will be joined into a combined analysis dataset. Relevant variables will be derived.
- The Danish scientific coordinator will assess the data validity of all countries by logical checks, examination of extreme values, and missing data. It is important that identification numbers are maintained to facilitate linkage back to the original datasets to be able to check the data and for the sake of transparency.

